- Serum microneutralization (MN) titers against RSV/A and B in maternal and infant subjects at select time-points may be generated for a subset of the population using the

derived/calculated endpoints previously referenced, based on geometric mean titer (GMT). An external laboratory, whose personnel are blinded to study treatment, will perform RSV/A and B MN testing during study conduct and after Day 180 unblinding. Final MN results, because of their time-consuming nature, may be provided as one or more sequential addenda to the main study report

Safety Endpoints:

In Infant Subjects:

• Percentages of term (≥ 37 weeks gestational age), healthy infants appropriate for gestational age (as determined by ultrasound gestational age assessment), APGAR scores, length, birth weight, frontal-occipital head circumference (FOC), and physical examination at birth.• Percentages of infants with AEs and SAEs (with special attention to congenital anomalies; respiratory failure other than RSV-associated hospitalization; neonatal death; infant death; sudden infant death syndrome; asphyxia; neonatal or hypoxic-ischemic encephalopathy; or other adverse events or complications of adverse events that necessitate hospitalization) during the neonatal period and through the first year of life.• Percentages of infants with unsolicited adverse events (including abnormalities detected in routine metabolic screening blood and neonatal hearing tests), unscheduled medical visits for adverse events, and serious adverse events through the first year of life.• Percentages of infants with developmental delay, as measured by the outcome of testing using a validated developmental scale at six months and at one year, in infants of RSV F vaccinees as compared to placebo.

In Maternal Subjects:

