At approximately 364 days after birth, all infants will participate in a study visit at home or in-clinic for evaluation of any AEs, MAEs, SNMCs, and SAEs experienced since the last visit; to record concomitant medications taken for these events; to report any healthcare provider-confirmed episodes of wheezing; and to report the mode of infant feeding, if a smoker or one or more children < 5 years of age reside in the same household, and whether the infant or another child in the household (< 5 years of age) is cared for in a group setting with other children (e.g., daycare) for ≥ 3 days per week. Infants will have a physical exam performed, and weight, length, and FOC measurements will be recorded. Developmental testing will be performed for all infant subjects. Note that parents/guardians of infant subjects with a positive screen detected at both 6 and 12 months of age (as this is an AE), or first appearing at 12 months of age, will be offered repeat Ages and Stages Questionnaire (ASQ)-3 screening at 15 and 18 months of age as a follow-up procedure. Novavax will collect this information as safety data. In addition, appropriate referrals for diagnostic pediatric developmental testing (according to local standards of care) will also be advised for infants with a positive screen identified. All procedures, including routine vaccinations that are considered standard of care for a corresponding baby-wellness visit, may be performed at this visit.

Parents/guardians may also be asked to consent to additional infant follow-up for future respiratory disease such as severe LRTI syndromes or recurrent wheezing. Such follow-up, if requested, will be voluntary and will be the subject of a separate future protocol and consent document.

Completion of this visit will mark the end of study participation for the infant subject.

Unscheduled Visits

Parents/guardians will be encouraged to report, or ask the infant's primary healthcare provider/pediatrician to report at any time, any other type of severe, serious, or otherwise concerning AE. If symptoms are presented that would require a physical exam to adequately assess potential AEs, the exam should be performed and vital signs collected.

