All safety endpoints will be summarized overall and by treatment group for maternal subjects and infant subjects based on Percentages of subjects experiencing an adverse event. Clinical laboratory data summaries for maternal subjects will include (by parameter and treatment group) toxicity grade shift summaries; absolute means and standard deviations with minima and maxima values, and tabulations of changes from baseline.

For infant subjects, summary statistics will be provided for infant length, weight, FOC, and responses to environmental and behavioral queries, through one year post-delivery overall, and by treatment group. Results of developmental testing will be summarized by treatment group, and Percentages of infants above normal, normal, at-risk at 6 or 12 months, and at-risk at both 6 and 12 months.

Immunogenicity analyses will be descriptive and include tabulations by treatment group for maternal subjects and infant subjects based on anti-F IgG, PCA, and RSV/A and RSV/B MN. The transplacental transfer of anti-F IgG, PCA, and RSV/A and RSV/B MN antibodies will be examined; first order modeling of their decay in infants will be performed for half-life estimations.

Exploratory Analyses:

Exploratory analysis will be conducted by generating classical two-by-two cross tabulations of all RSV respiratory tract infection endpoints detected by active/passive surveillance in infant and maternal subjects from immunization through six months after delivery and by treatment group. The relative risk (RR) and its 95% CI will be estimated using Poisson regression with robust error variance [Zou 2004]. A generalized linear model with unstructured correlation matrix (robust error variances)

will be used. The explanatory variables in the model will include the treatment group. The dependent variable will be the incidence rate. The Robust error variances will be estimated using repeated statement and the subject identifier. Poisson distribution will be used with a link function logarithm. The vaccine efficacy, and the corresponding two-sided 95% CI will be calculated.

Similar analysis will be conducted to assess the incidence of non-RSV LRTI in infant subjects as detected by active and passive surveillance from vaccination through six months after delivery. Percentages of infants and maternal subjects presenting with respiratory symptoms of non-RSV respiratory viruses detected by RT-PCR will be summarized.

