8.3.1 Ages and Stages Questionnaire

The Ages & Stages Questionnaires®, Third Edition (ASQ-3™) consists of a brief (10-15 minute) parent questionnaire that is then scored by health professionals. It is designed as a screening tool to pinpoint developmental progress in children between the ages of one month to 5 ½ years. One of the strengths of the ASQ is that it employs a parent-centric approach, although assistance by site staff is permissible (<http://agesandstages.com/>). Developmental assessments will be performed at 6 and 12 months (assessment for infants born prematurely may use age-appropriate adjusted scoring) of age for all infant subjects. For purposes of reporting the developmental screening as AEs, only abnormalities observed at both 6 and 12 months of age will be reported as an AE. Parents/guardians of infant subjects with a positive screen detected at both 6 and 12 months of age, or first appearing at 12 months of age, will be offered repeat ASQ screening of their infant at 15 and 18 months of age as a follow-up procedure. In addition, appropriate referrals for diagnostic pediatric developmental testing

(according to the local standards of care) will also be advised for infants with a positive screen identified.

As a guidance, *and solely for the purposes of consistency within this protocol*, it is suggested that investigators report ASQ abnormalities which persist at 6 and 12 months in a given infant as an AE that is “moderate” in severity. If diagnostic developmental testing is undertaken, the event should be further classified as a medically-attended event (MAE, see Section 8.4). If diagnostic evaluation, during the trial or afterward, leads to the diagnosis of a persistent developmental disability, the event then also becomes a serious adverse event (SAE, see Section 8.5) and should be reported as such.

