Summary statistics will also be provided for infant length, weight, FOC, and responses to environmental and behavioral queries, through one year post-delivery overall, and by treatment group. Results of developmental testing will be summarized by treatment group, and percentages of infants above normal, normal, at-risk at 6 or 12 months, and at-risk at both 6 and 12 months.

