10.10.3 Final Clinical Study Report (CSR)

The final CSR will include all efficacy, immunogenicity, and safety data (inclusive of clinical assessments and concomitant medications) through the infant subject's post-delivery study D+364 visit, the scheduled end of study. The database will be locked and the final study report prepared, when all of the above data have been entered, reviewed and all queries related to the data have been addressed.

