12.2. Analyses of Safety Objectives

Safety will be summarized for maternal and infant subjects separately. Safety will be summarized overall and by treatment group for maternal and infant subjects based on percentages.

Tabulations of counts and proportions of the following safety parameters, by treatment group and overall, will be produced for maternal subjects:

- Solicited seven-day reactogenicity events by severity;
- Clinical laboratory safety abnormalities by severity;
- Caesarean, vaginal, and instrument-assisted vaginal modes of delivery;
- Pre-specified third-trimester pregnancy and delivery complications (i.e., stillbirth, placental abruption, preterm birth, preterm premature rupture of membranes, hypertensive disorders of pregnancy, third-trimester hemorrhage, and gestational diabetes), and labor and delivery complications (i.e., emergency Caesarean section, postpartum hemorrhage, chorioamnionitis, and maternal fever or infection); and
- Unsolicited adverse events through 180 days post-delivery by severity and relatedness (possibly, probably, or definitely), including SAEs, MAEs, and SNMCs.

Tabulations of counts and proportions of the following safety parameters, by treatment group and overall, will be produced for infant subjects:

- Congenital anomalies; respiratory failure other than RSV-associated hospitalization; neonatal death; infant death; sudden infant death syndrome; asphyxia; neonatal or hypoxic-ischemic encephalopathy; or other adverse events or complications of adverse events that necessitate hospitalization during the neonatal period and through the first year of life;
- All other unsolicited/unspecified adverse events by severity, relatedness, and seriousness, including respiratory events that test negative for RSV by RT-PCR.

Summary statistics will also be provided for infant length, weight, FOC, 1- and 5-minute APGAR scores, and responses to environmental and behavioral queries, through one year post-delivery overall, and by treatment group. Results of developmental testing will be summarized by treatment group, and percentages of infants in the developmental testing subset above normal, normal, at-risk at 6 or 12 months, and at-risk at both 6 and 12 months.

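### The developmental-testing summary does not give the endpoint's six-month and one-year percentages, and it merges infants at risk only at 6 months with infants first at risk at 12 months

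*Protocol*

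**What the plan says.** The endpoint is time-specific. The Protocol Synopsis, Protocol 3.2.4.1 and SAP 4.3.1 all define it as "Percentages of infants with developmental delay, as measured by the outcome of testing using a validated developmental scale at six months and at one year", compared between infants of vaccinees and infants of placebo recipients.

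The planned tabulation is not. The Synopsis (Analyses of Safety and Immunogenicity Objectives) lists "Percentages of infants above normal, normal, at-risk at 6 or 12 months, and at-risk at both 6 and 12 months". Protocol 10.6 repeats this: "Results of developmental testing will be summarized by treatment group, and percentages of infants above normal, normal, at-risk at 6 or 12 months", followed by the at-both category. SAP 12.2 has the same rows but restricts them to a subset: "percentages of infants in the developmental testing subset above normal, normal, at-risk at 6 or 12 months, and at-risk at both 6 and 12 months".

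Three other provisions bear on how the rows are read:

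- The D+364 visit text (Synopsis and Protocol 6.1.2.9) singles out infants positive at both ages and infants newly positive at one year. A positive screen "first appearing at 12 months of age, will be offered repeat Ages and Stages Questionnaire (ASQ)-3 screening at 15 and 18 months of age". Infants positive only at 6 months are not in that offer.
- Protocol 8.3.1 sets the adverse-event rule: "only abnormalities observed at both 6 and 12 months of age will be reported as an AE".
- Protocol 10.10.3 describes the final study report as covering data "through the infant subject's post-delivery study D+364 visit, the scheduled end of study".

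**The concern.** A SAP's category list is what gets programmed. Here the list does not produce the quantity that the endpoint names. It also puts two clinically different groups in one row: infants whose 6-month flag had cleared by 12 months, and infants who were unremarkable at 6 months and newly flagged at one year. The protocol treats the second group as needing repeat screening.

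If maternal vaccination had an effect on development that showed only at one year, it would sit in that second group. In the planned summary it would be averaged with 6-month-only positives, and the adverse-event tables would not pick it up under the both-ages rule. At stake is the readability of a stated infant safety outcome in a maternal-vaccine trial. The efficacy conclusion is not affected.

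**Working it through.** **Can the endpoint be recovered from the listed rows?** In one arm, let *a* be the proportion at risk at 6 months only, *b* at 12 months only, and *c* at both.

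- Endpoint: six-month percentage = *a + c*; one-year percentage = *b + c*.
- Planned rows: *c*, plus either *a + b* (if the 6-or-12 row means one age only) or *a + b + c* (if it means at least one age).
- Under either reading the rows fix *a + b* and *c*, and nothing separates *a* from *b*. For example, *a* = 10%, *b* = 2% and *a* = 2%, *b* = 10% both print 12% in the one-age row, while the one-year percentage differs by 8 points (2% + *c* against 10% + *c*).
- If the one-year percentage were also tabulated, *b* would follow as (*b + c*) − *c*. The analysis text does not list it.

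This part needs no assumed rate.

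**How much could merging dilute a 12-month-only difference?** The documents give no ASQ-3 at-risk rates, so every rate below is an assumption. The 6-month-only rate is taken as equal in the two arms, and the whole effect is placed in the 12-month-only group. Arm sizes are the per-protocol estimates in Protocol 10.8: 2,786 vaccine and 1,432 placebo.

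Formula: z = (p_v − p_p) / √[p_v(1 − p_v)/n_v + p_p(1 − p_p)/n_p].

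Worked case, 10% at 6 months only, 4% versus 2% newly at risk at 12 months:

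- Separate row: √(0.04×0.96/2,786 + 0.02×0.98/1,432) = 0.00524; z = 0.02/0.00524 = 3.82; ratio 2.0.
- Merged row, 14% versus 12%: √(0.14×0.86/2,786 + 0.12×0.88/1,432) = 0.01081; z = 0.02/0.01081 = 1.85; ratio 1.17.

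| 6-month only, both arms | 12-month only, vaccine vs placebo | Separate: ratio, z | Merged: ratio, z |
|---|---|---|---|
| 10% | 4% vs 2% | 2.00, 3.82 | 1.17, 1.85 |
| 8% | 3.5% vs 2% | 1.75, 2.95 | 1.15, 1.50 |
| 15% | 5% vs 3% | 1.67, 3.27 | 1.11, 1.58 |
| 5% | 3.5% vs 2% | 1.75, 2.95 | 1.21, 1.75 |
| 5% | 4% vs 2% | 2.00, 3.82 | 1.29, 2.31 |

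Safety summaries use the Safety Population, which is somewhat larger. With the enrolment targets of about 3,038 and 1,562 mothers as an upper guide, the first scenario becomes 0.02/0.00502 = 3.99 separate and 0.02/0.01036 = 1.93 merged. The pattern is unchanged.

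The dilution depends on the assumed rates. For a doubling of 12-month-only risk, 2% at 6 months only and 3% new onset give a merged ratio of (2 + 6)/(2 + 3) = 1.60. With 10% and 1% it is (10 + 2)/(10 + 1) = 1.09.

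**The case against.** The strongest reply is that the endpoint definition itself calls for a one-year percentage against placebo, and the Synopsis says all safety endpoints are summarized by treatment group. The sentence with the categories can be read as adding to such a summary. The above-normal and normal rows look like results of a single assessment, since no rule says how to combine two ages, so the list may be shorthand for by-visit tables. That is possible. But the same list appears in all three analysis passages and none of them names a by-age percentage, so the text still has to be made to match the endpoint.

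A reader might go further and infer that delay first appearing at one year is never compared by arm, or cannot be seen anywhere. The documents do not support that:

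- The merged row contains these infants and is shown by arm.
- SAP 16.6 places all eCRF data in listings that accompany the study report.
- Protocol 8.3.1 makes a diagnosed persistent disability an SAE, although that needs a completed diagnosis and is less sensitive than the screen.
- Protocol 8.3 and SAP 12.4 name abnormal developmental tests among possible infant adverse events without the both-ages condition, which conflicts with 8.3.1.

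Nor does Protocol 10.10.3 bar the 15- and 18-month results from being reported. It states what the final report includes. Those screens are only offered, and only to infants with qualifying positives, so a by-arm comparison of them would be selective.

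Two limits on the numbers also stand. All rates are assumed, and no hypothesis test is planned for this descriptive summary, so z is only a gauge of visibility.

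**Conclusion.** The point holds as a mismatch between endpoint and tabulation. The listed rows give neither the six-month nor the one-year percentage, and they merge 6-month-only with 12-month-only infants. The second group is not an adverse event under the rule in Protocol 8.3.1. It is diluted rather than wholly unreported.

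The mismatch rests on the text alone. The size of the dilution is illustrative: across the five scenarios (5–15% at risk at 6 months only, new-onset ratios of 1.67–2.0, per-protocol arm sizes), z is about 2.95–3.8 in a separate row and about 1.5–2.3 in the merged row. These are not bounds, and other assumed rates give more or less dilution. The change is worth making because the endpoint is stated and the data exist.

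**What to change.** In the Protocol Synopsis, Protocol 10.6 and SAP 12.2, replace the category list with a by-arm cross-classification of the 6-month and 12-month ASQ-3 results in the infant Safety Population. Report:

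- at risk at 6 months and at risk at 12 months, each with infants tested at that age as denominator;
- at risk at 6 only, at 12 only, and at both, with infants tested at both ages as denominator;
- the vaccine–placebo difference with a 95% CI for each.

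Reconcile two sets of passages in the same edit: the developmental testing subset in SAP 12.2 with the testing of all infants in Protocol 6.1.2.9 and 8.3.1, and Protocol 8.3 (with SAP 12.4) with 8.3.1 on when an abnormal developmental test is an adverse event. A listing of the 15- and 18-month repeat screens is optional.

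The cost is a wording change and one table from data already collected. No new data or subjects are needed.

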1 INTRODUCTION

1.1 Respiratory Syncytial Virus (RSV) Background

Respiratory syncytial virus (RSV) is the leading viral cause of severe lower respiratory tract disease in infants and young children worldwide. The World Health Organization (WHO) has estimated that the global annual burden of infections and mortality due to human RSV are 64 million and 160,000, respectively [WHO 2009]. In industrialized countries, nearly all children have been infected with RSV by 2 years of age. Most infected children present with mild upper respiratory tract symptoms, but a subset develops severe lower respiratory tract disease characterized by tachypnea, hyperinflation, crackles, and expiratory wheezing (i.e., bronchiolitis and pneumonia). The most severe disease occurs within the first 2 to 8 months of life, particularly in infants born prematurely and infants with underlying chronic lung and congenital heart diseases.

Immunity to RSV remains incomplete and frequent reinfections occur throughout life, with the frail elderly, immunocompromised, and those with underlying cardiopulmonary disorders being among the most susceptible to severe disease in the adult population. It is estimated that between 11,000 to 17,000 elderly adults die of RSV infection or its complications annually in the US, with approximately ten-fold more admitted to the hospital with respiratory symptoms [Walsh 2012]. Actual attack rates may be higher still, as an RSV diagnosis is often not made in adults unless highly sensitive molecular diagnostic tests (i.e., RT-PCR) are performed. Acute respiratory illness due to RSV has been documented in previously healthy immunocompetent adults as well (e.g., military recruits), although the clinical severity of infection or subsequent re-infection is typically diminished [O'Shea 2007].

RSV is a pleomorphic virus belonging to the *Paramyxoviridae* family, and comprises two major subtypes, A and B, that co-circulate. The two major surface glycoproteins of RSV, F and G, are the primary targets of neutralizing antibodies, which are associated with protection [Graham 2011]. The F protein mediates fusion of the viral envelope with the plasma membrane and syncytium formation, while the G protein is essential for viral attachment. There is a high degree of genetic and antigenic homology in the F proteins across RSV/A and B viruses, and among individual isolates, whereas the G protein is much more variable [Johnson 1987]. Immunization with vaccinia virus containing the F gene protected animals against homologous and heterologous subtype A and B viral challenge; whereas, animals immunized with the G gene expressed in the same system were only protected against the homologous virus [Olmsted 1986, Stott 1987]. These data demonstrate the ability of anti-F neutralizing antibodies to generate immunity across RSV/A and B subtypes.

1.2 Summary of RSV Disease in Various Geographies

1.2.1 High-resource Countries in the Northern and Southern Hemispheres

Data from the United States (US) and Australia suggest that 1.7 to 2.6% of infants are hospitalized for RSV infection before 1 year of age [Hall 2009, Iwane 2004, Ranmuthugala 2011]. Annually in the US, RSV infection is associated with an estimated 57,527 hospitalizations and 2.1 million outpatient visits among children < 5 years of age

[[Centers for Disease Control and Prevention \(update May 05 2015\)](#), [Hall 2009](#)]. In the US, Native American children are at increased risk for RSV infection. In 2000-2001, the rate of RSV hospitalization among Native American children <1 year of age in the southwest US was 48 per 1000, nearly double the rate of similarly aged children in the general US population (27 per 1000) [[Holman 2004](#)]. Among Native American infants in the southwest US, 11% of healthy babies were hospitalized with RSV in their first year of life. [[O'Brien 2015](#)] The elevated risk of admission - roughly six-fold that of infants in the general US population - is probably related to socioeconomic and geographic conditions [[Bockova 2002](#)].

In the United Kingdom (UK), over the winter seasons from 1989 to 2000, the average annual RSV-associated mortality in infants 1 to 12 months of age was 8.4 per 100,000 population [[Fleming 2005](#)]. The clinical manifestations and morbidity of RSV are similar among infants and young children worldwide, regardless of the country of residence. However, the majority of deaths due to RSV still occur in developing countries, where burden and risk factors for life-threatening illness remain the greatest. In fact, mortality rates due to RSV are difficult to ascertain in many settings, because children in developing countries, where 99% of fatal cases occur [[Nair 2010](#)], often die at home [[Moisi 2011](#)].

